8.3.5 Causality collection

The Investigator will assess causal relationship between Investigational Product and each Adverse Event, and answer ‘yes’ or ‘no’ to the question ‘Do you consider that there is a reasonable possibility that the event may have been caused by the investigational product or combination drug?’

For SAEs, causal relationship will also be assessed for other medication and study procedures. Note that for SAEs that could be associated with any study procedure the causal relationship is implied as ‘yes’.

A guide to the interpretation of the causality question is found in Appendix B.

8.3.6 Adverse events based on signs and symptoms

All AEs spontaneously reported by the patient or care provider, reported in response to the open question from the study site staff: “Have you had any health problems since the previous visit/you were last asked?,” or revealed by observation will be collected and recorded in the CRF. When collecting AEs, the recording of diagnoses is preferred (when possible) to recording a list of signs and symptoms. However, if a diagnosis is known and there are other signs or

symptoms that are not generally part of the diagnosis, the diagnosis and each sign or symptom will be recorded separately.

8.3.7 Adverse events based on examinations and tests

The results from the protocol mandated laboratory tests and vital signs will be summarised in the clinical study report (CSR). Deterioration as compared to baseline in protocol-mandated laboratory values and vital signs should therefore only be reported as AEs if they fulfil any of the SAE criteria or are the reason for discontinuation of treatment with the investigational products.

If deterioration in a laboratory value/vital sign is associated with clinical signs and symptoms, the sign or symptom will be reported as an AE and the associated laboratory result/vital sign will be considered as additional information. Wherever possible the reporting Investigator uses the clinical, rather than the laboratory term (e.g., anaemia versus low haemoglobin value). In the absence of clinical signs or symptoms, clinically relevant deteriorations in non-mandated parameters should be reported as AE(s).

Deterioration of a laboratory value, which is unequivocally due to disease progression, should not be reported as an AE/SAE.

Any new or aggravated clinically relevant abnormal medical finding at a physical examination as compared with the baseline assessment will be reported as an AE unless unequivocally related to the disease under study, see sections 8.3.9 and 8.310.

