Temozolomide has activity in the relapsed / refractory setting for CRC, likely related to the high prevalence of MGMT promoter hypermethylation in this disease, which is supported by prospective clinical trials. Based on TMZ resistance mechanisms described, preliminary data suggests the addition of PARP inhibitors can lead to a sustained anti-tumor response and appropriate safety data to support this combination is available. Therefore we propose a biomarker driven, open-label clinical trial with TMZ in combination with the poly ADP ribose polymerase (PARP) inhibitor olaparib for MGMT promoter hypermethylated CRC.

Table 2. Objectives and endpoints:

Primary objectives:	Endpoints/variables:
To determine the efficacy of TMZ in combination with olaparib in subjects with MGMT promoter hypermethylated advanced colorectal cancer by the overall response rate (ORR)	ORR by RECIST v1.1 criteria

Secondary objectives:	Endpoints/variables:
To determine the safety of TMZ in combination with olaparib	Rate of \geq grade 3 adverse events by CTCAE v5.0
To estimate the progression free survival (PFS)	PFS
To estimate overall survival (OS)	OS
Exploratory objectives:	Endpoints/variables:
Characterize NGS profiling, patterns of DNA methylation, gene expression, and develop MGMT expression assays	Association of NGS profiling, patterns of DNA methylation, gene expression, and develop MGMT expression assays with efficacy and clinical parameters.
Correlate molecular features with γ H2AX with response	Association of γ H2AX with response rate and survival endpoints
Establish organoids for MGMT promoter hypermethylated colorectal cancer	Form a library of colorectal cancer organoids

Overall design:

This is a Phase II, non-randomized, open-label, single-institution study to evaluate temozolomide in combination with olaparib in patients with MGMT promoter hypermethylated advanced colorectal cancer. Potentially eligible patients will be tested for MGMT promoter hypermethylation by methylation specific PCR after signing a pre-screening consent. The study will begin with a safety evaluation period to assess for dose limiting toxicity (DLT) in the first 6 treated patients, and if toxicity is observed a dose de-escalation schema will be considered.

Study period:

Estimated Date of First Patient Enrolled: January 2020

Estimated Date of Last Patient Completed: January 2022

Number of patients:

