Data from studies of olaparib in combination with various chemotherapy agents indicate an increase in bone marrow toxicity (anaemia, neutropenia, thrombocytopenia) greater than expected if the agents had been administered alone. The effects are generally transient but treatment delays are common and alternative administration schedules/toxicity management processes are currently being evaluated within some of these studies. When this type of toxicity has occurred it has been managed by routine clinical practice including dose delays, dose reductions, intermittent dosing and/or the use of supportive care measures, including G-CSF. Currently, all ongoing olaparib combination studies are being closely monitored for myelotoxicity. Results of a Phase II study in combination with carboplatin/paclitaxel (Study D0810C00041) showed that addition of olaparib to carboplatin AUC 4 + paclitaxel in the chemotherapy phase had a generally similar tolerability profile to carboplatin AUC 6 + paclitaxel. The regimen of olaparib capsules 200 mg bd for 10 days out of 21, with carboplatin AUC 4 + paclitaxel had an acceptable and manageable tolerability profile in patients with recurrent serous ovarian cancer. Olaparib tolerability during the monotherapy maintenance phase was consistent with the previously known safety and tolerability profile. In Study D0810C00039 and Study D081BC00004, olaparib 100 mg tablet bd in combination with weekly paclitaxel 80 mg/m² was well tolerated, with no new unexpected safety findings. In both studies, the incidence of neutropenia was higher for the olaparib combination arm and this contributed to higher rates of dose modifications for patients on olaparib compared to placebo. In Study D081BC00004, there was also a higher incidence of anaemia on the olaparib + paclitaxel combination arm than on the placebo + paclitaxel arm and more dose interruptions, reductions and discontinuations.

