3. OBJECTIVES AND ENDPOINTS

Hypothesis: We hypothesize that MGMT promoter hypermethylation will sensitize tumors to the combination of temozolomide with the PARP inhibitor olaparib.

Primary Objectives:

- To determine the efficacy of TMZ in combination with olaparib as measured by the overall response rate.

Secondary Objectives:

- To determine the safety of TMZ in combination with olaparib.
- To estimate progression free survival (PFS).
- To estimate overall survival (OS).

Exploratory Objectives:

- Identify patterns of next generation sequencing analysis, DNA methylation, mutational load and gene expression in MGMT promoter hypermethylated colorectal cancer.
- Correlate molecular features with markers of DNA damage including γ H2AX phosphorylation levels.
- Establish organoids for MGMT promoter hypermethylated colorectal cancer.

Primary Endpoints:

- Objective response rate by RECIST v1.1 criteria for combined therapy with temozolomide and olaparib.

Secondary Endpoints:

- Progression free survival.
- Overall survival.
- Rate of \geq grade 3 adverse events.

Exploratory Endpoints:

- Association of NGS profiling, patterns of DNA methylation, gene expression, and develop MGMT expression assays with efficacy and clinical parameters.
- Association of γ H2AX with response rate and survival endpoints.
- Form a library of colorectal cancer organoids

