8.2.1 Clinical safety laboratory assessments

Blood and urine samples for determination of clinical chemistry, hematology, and urinalysis will be taken at the times indicated in the assessment schedules and as clinically indicated (see the SoAs).

Clinical laboratory safety tests, including serum pregnancy tests, will be performed in a licensed clinical laboratory according to local standard procedures. Sample tubes and sample sizes may vary depending on the laboratory method. Urine pregnancy will be performed using a licensed test (urine or serum pregnancy tests are acceptable). Abnormal clinically significant laboratory results should be repeated as soon as possible.

Additional safety samples may be collected if clinically indicated at the discretion of the investigator. The date, time of collection, and results (values, units, and reference ranges) will be recorded in the appropriate eCRF.

The laboratory variables to be measured are presented in Table 10 (clinical chemistry and hematology).

Table 10 **Laboratory safety variables**

Haematology/Haemostasis (whole blood)	Clinical Chemistry (serum or plasma)
B-Haemoglobin (Hb)	S/P-Creatinine
B-Leukocyte count	S/P-Bilirubin, total
B-Absolute neutrophil count	S/P-Alkaline phosphatase (ALP)
B-Absolute lymphocyte count	S/P-Aspartate transaminase (AST)
B-Platelet count	S/P-Alanine transaminase (ALT)
B-Mean cell volume (MCV)	S/P-Albumin
	S/P-Potassium
	S/P-Calcium, total
	S/P-Sodium
Urinalysis (macroscopic w/reflex microscopic)	S/P-Urea or Blood Urea Nitrogen (BUN)
U-Hb/Erythrocytes/Blood	S/P-Total Protein
U-Protein/Albumin	
U-Glucose	

NB. In case a patient shows an AST **or** ALT $\geq 3 \times \text{ULN}$ together with total bilirubin $\geq 2 \times \text{ULN}$ please refer to Appendix A. Actions required in cases of increases in liver biochemistry and evaluation of Hy's Law', for further instructions.

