8.4.5 Management of adverse events related to Olaparib and TMZ

Any toxicity observed during the course of the study could be managed by interruption of the dose of the attributed study treatment or dose reductions. Repeat dose interruptions are allowed as required, for a maximum of 4 weeks on each occasion. If the interruption is any longer, the study team must be informed. Olaparib treatment can be dose reduced to 100 mg twice daily. If the reduced dose of 100 mg twice daily is not tolerable, olaparib can be further dose reduced to 100 mg daily, and if this is not tolerable no further dose reduction is allowed and study treatment should be discontinued. Temozolomide can be dose reduced to 60 mg/m² (Days 1-7), and if this is not tolerable TMZ can be further dose reduced to 50 mg/m² (Days 1-7). The following tables should be applied if an AE is deemed to be at least “possibly related” to olaparib, TMZ, or both. If an AE is only attributed to one of the agents the other agent may be continue at an unadjusted dose.

Once dose is reduced, escalation is not permitted (except following concomitant treatment with CYP3A4 inhibitors – see Section 6.5

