CTCAE Grade 1-2	Investigator judgement to continue treatment or if dose interruption, this should be for a maximum of 4 weeks; appropriate supportive treatment and causality investigation
CTCAE Grade 3-4*	Dose interruption until recovered to CTCAE gr 1 or better for a maximum of 4 weeks. If repeat CTCAE grade 3-4 occurrence, dose reduce olaparib to 100 mg twice daily as a first step and 100 mg once daily as a second step and dose reduce TMZ to 60 mg/m² as a first step and 50 mg/m² as a second step.

* If the starting dose of TMZ is lowered as described in section 4.2 the TMZ dose should be lowered per table 7 based on the starting dose.

Adverse event of neutropenia and leukopenia should be managed as deemed appropriate by the investigator with close follow up and interruption of study drug if CTCAE grade 3 or worse neutropenia occurs.

Primary prophylaxis with Granulocyte colony-stimulating factor (G-CSF) is not recommended, however, if a patient develops febrile neutropenia, study treatment should be stopped and appropriate management including G-CSF should be given according to local hospital guidelines. Please note that G-CSF should not be used within at least 24 h (7 days for pegylated G-CSF) of the last dose of TMZ or olaparib unless absolutely necessary.

Platelet transfusions, if indicated, should be done according to local hospital guidelines.

For cases where patients develop prolonged haematological toxicity (≥ 2 week interruption/delay in study treatment due to CTCAE grade 3 or worse), refer to guidance later in this section for the management of this.

Management of prolonged haematological toxicities while on study treatment

If a patient develops prolonged haematological toxicity such as:

- ≥ 2 week interruption/delay in study treatment due to CTCAE grade 3 or worse anaemia and/or development of blood transfusion dependence
- ≥ 2 week interruption/delay in study treatment due to CTCAE grade 3 or worse neutropenia ($ANC < 1 \times 10^9/L$)
- ≥ 2 week interruption/delay in study treatment due to CTCAE grade 3 or worse thrombocytopenia and/or development of platelet transfusion dependence (Platelets $< 50 \times 10^9/L$)

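### Section 8.3.7 lets asymptomatic, transient Grade 3-4 neutropenia, leukopenia or thrombocytopenia go unrecorded as an AE, so the Grade 3+ adverse event rate can come out too low

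*Combined protocol and SAP*

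**What the plan says.** Table 2 in the Synopsis sets the safety endpoint as the rate of events at or above "grade 3 adverse events by CTCAE v5.0". Section 3 repeats it. No other secondary endpoint covers safety.

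Section 8.3.7 decides which laboratory findings become adverse events. Results of mandated tests are to be summarised in the study report, and a deterioration in them "should therefore only be reported as AEs if they fulfil any of the SAE criteria or are the reason for discontinuation of treatment". If there are symptoms, the symptom is the AE and the laboratory result is supporting information. Deterioration without symptoms is reportable only for parameters that are not mandated. CTCAE grade is not a trigger.

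The complete blood count with differential is in the Schedule of Activities. Neutrophils, leukocytes and platelets are in Table 10 (section 8.2.1).

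For Grade 3-4 neutropenia, leukopenia or thrombocytopenia, Table 12 (section 8.4.5.1) prescribes "Dose interruption until recovered to CTCAE gr 1 or better for a maximum of 4 weeks", with dose reduction on recurrence. Discontinuation follows if counts do not recover within 4 weeks.

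Section 9.4.1 compares toxicity rates with established rates and gives 95% confidence intervals. Section 9.4.2 tabulates AEs and, as a further item, lists Grade 3 and 4 laboratory abnormalities.

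**The concern.** The endpoint counts adverse events, and section 8.3.7 keeps one class of high-grade toxicity from being recorded as such. That class matters here. Section 2.3.1 reports, for olaparib combined with chemotherapy, "an increase in bone marrow toxicity (anaemia, neutropenia, thrombocytopenia) greater than expected if the agents had been administered alone".

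Two consequences follow. First, the Grade 3+ rate can understate the toxicity the trial most expects. Second, recording may differ between investigators, because other text treats the same finding as an AE. Appendix B1 gives an abnormal laboratory finding as an example of an AE. Section 8.4.5 introduces its management tables with "The following tables should be applied if an AE is deemed to be at least" possibly related to treatment. Section 8.4.5.1 begins an instruction with "Adverse event of neutropenia and leukopenia should be managed as deemed appropriate by the investigator". One investigator following section 8.3.7 and another following section 8.4.5 could record the same asymptomatic Grade 3 neutropenia differently.

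The comparison in section 9.4.1 is also affected. The documents do not say whether the established rates count laboratory events, so it cannot be checked whether like is compared with like.

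**Working it through.** The plan states no expected rate, precision or threshold for this endpoint, so there is no figure to reproduce. The check follows one case through the rules and then shows what one lost patient is worth.

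**Step 1. Trace an asymptomatic Grade 3 neutropenia that recovers in under 4 weeks.**

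- Mandated test? Yes (Schedule of Activities, Table 10), so the restriction in section 8.3.7 applies.
- Symptom route? No, there are none.
- Discontinuation route? No. Table 12 interrupts treatment, and discontinuation follows only on non-recovery.
- SAE route? Not clearly. Appendix B5 gives blood dyscrasias as examples of important medical events, but the wording is unclear for neutropenia without transfusion, leukopenia and thrombocytopenia are not named, and the decision rests on medical judgement.
- Result: section 8.3.7 does not call for an AE record, so the patient is not counted unless another Grade 3+ AE is recorded.

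**Step 2. Mark the limits of the gap.**

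- Transfused anaemia is mostly captured: Table 11 provides for transfusion, and Appendix B5 says such events should usually be treated as serious.
- Febrile neutropenia is mostly captured through symptoms, seriousness or stopping of treatment.
- Counts that do not recover are captured through discontinuation.
- Section 4.3 counts Grade 4 haematological toxicity as dose limiting (neutropenia only if it lasts 7 days or more), but only in cycle 1 of the safety evaluation period. That count is not the endpoint.

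**Step 3. Effect of one uncounted patient.** Change in rate = -1/N, where N is the number in the Safety Analysis Set (all who receive any study drug; section 9.3).

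- N = 30, the planned evaluable number: 1/30 = 0.033, or 3.3 percentage points.
- N = 9, a stop at stage 1: 1/9 = 0.111, or 11.1 points.

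Both values of N are assumptions. Non-evaluable patients may be replaced (section 9.2), and after a dose reduction up to 30 evaluable patients are treated at the reduced dose in addition to those already treated (section 4.2). Either raises N and lowers 1/N.

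**Step 4. Illustration under assumed values.** Let T be the true share of patients with any Grade 3+ event, and f the share of those patients whose only such event is an unreported count. Neither is in the documents. Expected observed rate = T × (1 - f).

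| T | f = 0.10 | f = 0.25 | f = 0.50 |
|---|---|---|---|
| 40% | 36% | 30% | 20% |
| 50% | 45% | 37.5% | 25% |
| 60% | 54% | 45% | 30% |

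Over this grid the error runs from -4 points (40% to 36%) to -30 points (60% to 30%). At T = 50% and n = 30, the Wilson 95% interval is 33.2% to 66.8% with full counting and 22.5% to 55.3% with f = 0.25. The grid shows sensitivity only; it does not estimate what this trial will see.

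**The case against.** The strongest reply is that the protocol runs two streams on purpose: AEs are tabulated, and Grade 3-4 laboratory abnormalities are listed beside them. A reader of the report would see both. On that view the rate is not biased; its definition is merely unclear, and the toxicity rates in section 9.4.1 could be read to include laboratory values. Moreover:

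- Reasons for every interruption go in the eCRF (section 8.4.5.2), so cases managed under Table 12 can be traced.
- The safety review in section 9.5.2 includes laboratory data.
- The AE language in section 8.4.5 may lead sites to record these events anyway.
- No hypothesis or stopping rule uses this rate.
- If the established rates come from AE records alone, the present rate already matches them.

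Much of this stands. The data are recoverable, the response endpoint is untouched, and no size can be established. But a listing does not enter a proportion or its confidence interval, and no text places the listed values in the numerator. If sites do record these events, they depart from section 8.3.7, and the rate then depends on habit. The uncertainty about the established rates is a reason to report both versions.

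It can also be said that grading all mandated tests reaches beyond three cytopenias. It does, but section 8.3.7 restricts all of them alike.

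**Conclusion.** The concern holds. Followed as written, section 8.3.7 allows a transient, asymptomatic Grade 3-4 neutropenia, leukopenia or thrombocytopenia to be left out of the Grade 3+ adverse event rate. The effect is downward or zero, because the rule can only remove events. It is zero if every affected patient also has another recorded Grade 3+ event, or if sites record these counts as AEs despite the rule.

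The total size is unknown. The per-patient figures of 3.3 and 11.1 points rest on 30 and 9 treated patients and shrink if more are treated. This should be corrected before the safety analysis. It does not affect the response analysis or the futility rule.

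**What to change.** - In Table 2, section 3 and section 9.4.2, define the endpoint as the proportion of the Safety Analysis Set with at least one treatment-emergent CTCAE v5.0 Grade 3 or higher event. Treatment-emergent means onset, or worsening in grade from baseline, between first dose and 30 days after last dose.
- Take events from AE records or from programmed grading of the mandated laboratory values. Keep the exclusion in section 8.3.7 for deterioration unequivocally due to progression.
- Report the AE-record-only rate alongside, so that the comparison in section 9.4.1 can use the version that matches how the established rates were counted. State which version that is.
- Reconcile section 8.3.7 with sections 8.4.5 and 8.4.5.1 and Appendices B1 and B5 on when a laboratory cytopenia is recorded as an AE.

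Baseline is simple for two of the counts. Eligibility requires neutrophils of at least 1.5 and platelets of at least 100 × 10⁹/L, while section 8.4.5.1 places Grade 3 below 1 and below 50. For a patient who meets these criteria at baseline, any Grade 3+ value on treatment is a worsening.

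The cost is wording plus programming on data already collected. No test is added and no management rule changes. There are two downsides: values that may reflect progression, such as liver tests in patients with liver metastases, will need case review, and the reported Grade 3+ rate may be higher.

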8.3.8 Hy's law

Cases where a patient shows elevations in liver biochemistry may require further evaluation and occurrences of AST or ALT $\geq 3 \times \text{ULN}$ together with total bilirubin $\geq 2 \times \text{ULN}$ may need to be reported as SAEs. Please refer to Appendix A for further instruction on cases of increases in liver biochemistry and evaluation of Hy's Law

8.3.9 Disease progression

Disease progression can be considered as a worsening of a patient's condition attributable to the disease for which the investigational product is being studied. It may be an increase in the severity of the disease under study and/or increases in the symptoms of the disease. The development of new, or progression of existing metastasis to the primary cancer under study should be considered as disease progression and not an AE. Events, which are unequivocally due to disease progression, should not be reported as an AE during the study.

8.3.10 New Cancers

The development of a new primary cancer should be reported as an AE (see Section 8.3.13 Olaparib Adverse Events of Special Interest) and would in most cases meet seriousness criteria (with the exception of some non-melanoma skin cancers). New primary malignancies are those that are not the primary reason for the administration of the study treatment and have developed after the inclusion of the patient into the study. They do not include metastases of the original cancer. Symptoms of metastasis or the metastasis itself should not be reported as an AE/SAE, as they are considered to be disease progression.

